6.3.6 Progression-Free Survival

Progression-Free Survival: Progression free survival will be defined from the time of registration to the time of confirmed progression. In cases where this might be unclear, patients may continue on trial.

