2.3 PARTICIPANT REGISTRATION AND STATUS UPDATE PROCEDURES

Registration and status updates (e.g., when a participant is taken off protocol therapy and when a participant is taken off-study) will take place per CCR SOP ADCR-2, CCR Participant Registration & Status Updates found [here](#).

2.3.1 Treatment Assignment Procedures (For registration purposes only):

Cohorts

Number	Name	Description
1	Cohort 1	Subjects with intra-cranial or spinal RELA -fusion ependymoma who have had none, 1 or 2 prior chemotherapies.
2	Cohort 2	Subjects with intra-cranial or spinal RELA -fusion ependymoma who have had more than 2 prior chemotherapies.
3	Cohort 3	Subjects with intra-cranial or spinal non RELA -fusion ependymoma who have had none, 1 or 2 prior chemotherapies.
4	Cohort 4	Subjects with intra-cranial or spinal non RELA -fusion ependymoma who have had more than 2 prior chemotherapies.
P	Cohort P	Children who may have been exposed to the study drug in utero OR expectant mothers of children who may have been exposed to the study drug in utero if mother not in a treatment cohort

Arm

Number	Name	Description
1	Arm 1	Marizomib at days 1, 8 and 15 of each 28-day cycle
P	Pregnancy evaluation	Data collection on pregnancy, birth and health of child up to 1 year.

Arm assignment

Subjects in Cohort 1, 2, 3 and 4 will be directly assigned to Arm 1.

Subjects in Cohort P will be directly assigned to Arm P.

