6.3.3 RANO Disease Response Criteria

For the purposes of this study, patients should be re-evaluated for response every 8 weeks. Confirmatory scans should also be obtained in 4-8 weeks period of time following initial documentation of objective response.

Table 6: RANO Criteria for Response

RANO Criteria for Response (28)	CR	PR	SD	PD
T1 gadolinium enhancing disease	None	≥ 50% ↓	< 50% ↓ but < 25% ↑	≥ 25% ↑ ¹
T2/FLAIR	Stable or ↓	Stable or ↓	Stable or ↓	↑ ¹
New lesion	None	None	None	Present ¹
Corticosteroids	None	Stable or ↓	Stable or ↓	n/a [†]
Clinical status	Stable or ↑	Stable or ↑	Stable or ↑	↓ ¹
Requirement for response	All	All	All	Any ¹

RANO Criteria for Response (28)				
	CR	PR	SD	PD

¹ Progression occurs when this criterion is present
 
† Increase in corticosteroids alone will not be taken into account in determining progression in the absence of persistent clinical deterioration.
 
↓ = decreased, ↑ = increased,
 
CR = complete response, PR = partial response, SD = stable disease, PD = progressive disease. If PD is unclear based on white matter changes, patients may be kept on trial.
 
FLAIR, fluid-attenuated inversion recovery; NA, not applicable.
				

Stable/No Progression (SD): No evidence of new measurable lesions on MR imaging. The designation of Stable/No Progression requires a minimum of 12 weeks duration. All measurable and evaluable sites must be assessed using the same techniques as baseline.

Partial response (PR): ≥ 50% reduction in the sum of products of all measurable lesions over baseline sum observed using the same techniques as baseline. The patient must be on a stable or decreased dose of corticosteroids to be evaluable for response.

Complete response (CR): Complete resolution of all lesions. The patient cannot be on any corticosteroids with the exception of adrenal replacement doses.

Progression (PD): 25% increase in the sum of products of all measurable lesions over smallest sum observed (over baseline if no decrease) using the same techniques as baseline, OR clear worsening of any evaluable disease, OR appearance of any new lesion/site, OR failure to return for evaluation due to death or deteriorating condition (unless clearly unrelated to this cancer).

Unknown: Progression has not been documented and one or more measurable or evaluable sites have not been assessed.

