6.3.7 Overall survival

Overall survival: Defined as the time from registration to the time of death

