Table 7. Operating characteristics of the two-stage sequential enrichment design

True PFS6 of RELA -fusion ependymomas	True PFS6 of	Probability of early stopping	Probability of claiming	Probability of claiming	Average sample size

	Non RELA- fusion ependymomas		effective for RELA -fusion	effective for all patients	
0.3	0.3	0.734	0.265	0.016	13.2
0.6	0.6	0.102	0.898	0.796	23.4
0.6	0.3	0.102	0.898	0.167	23.4
0.6	0.5	0.102	0.898	0.632	23.4

The study of salvage cohorts 2 and 4 is a secondary objective.

As patients in salvage cohorts 2 and 4 are highly heterogeneous, the efficacy of marizomib in *RELA*-fusion cohort 2 may not be notably higher than that in non *RELA*-fusion cohort 4. The objective of cohorts 2 and 4 is to estimate the efficacy of marizomib in recurrent ependymoma patients with multiple prior chemotherapies as measured by PFS6, PFS12, median PFS and OS. As a result, the 2-stage design will not be used for cohorts 2 and 4. Instead, we enroll patients into these cohorts simultaneously.

10.1.1 Primary Endpoint:

- Progression-free survival at 6 months of *RELA*-fusion and non *RELA*-fusion recurrent ependymoma patients treated with marizomib (Cohorts 1-4) will be assessed as proportion of patients that are progression-free at 6 months timepoint after initiation of treatment.

10.1.2 Secondary Endpoint(s):

- Progression-free survival at 12 months of *RELA*-fusion and non *RELA*-fusion recurrent ependymoma patients treated with marizomib (Cohorts 1-4) will be assessed as proportion of patients that are progression-free at 12 months timepoint after initiation of treatment
- Median progression-free survival (PFS) of *RELA*-fusion and non *RELA*-fusion recurrent ependymoma patients treated with marizomib (Cohorts 1-4) will be assessed as median amount of time subject survives without disease progression after initiation of treatment
- Overall survival (OS) of *RELA*-fusion and non *RELA*-fusion recurrent ependymoma patients treated with marizomib (Cohorts 1-4) will be assessed as median amount of time subject survives after initiation of therapy
- Progression-free survival at 6 months of *RELA*-fusion and non *RELA*-fusion recurrent ependymoma patients with with more than 2 prior chemotherapies treated with marizomib (Cohorts 2 and 4) will be assessed as proportion of patients that are progression-free at 6 months timepoint after initiation of treatment.

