10.4 STATISTICAL ANALYSES

10.4.1 Analysis of the Primary Endpoint:

Kaplan-Meier curve will be used to estimate the PFS6 for *RELA*-fusion and non *RELA*-fusion recurrent ependymoma. We will calculate mean, standard deviation and 95% confidence interval of PFS6. Logrank test and proportional hazard model will be used to compare the PFS between *RELA*-fusion and non *RELA*-fusion recurrent ependymoma.

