10.4.4 Planned Interim Analyses

Two-stage sequential enrichment design will be used for this trial. In the first stage, we will enroll 9 patients with *RELA*-fusion ependymomas (Cohort 1) to test for clinical activity of marizomib. If 4 or more patients are progression free at 6 months, we proceed to stage 2; otherwise we terminate the trial and conclude that marizomib is not effective. At stage 2, we will enroll 32 patients with non *RELA*-fusion ependymomas (Cohort 3 and 4). From Cohort 3, if 9 or more of 16 patients are progression free at 6 months, we claim that marizomib is promising for treating both *RELA*-fusion and non *RELA*-fusion ependymoma; otherwise, we claim that marizomib is promising for treating *RELA*-fusion, but not for non *RELA*-fusion ependymoma. As above, PFS-6 for Cohort 4 will also be measured in patients with non-*RELA* fusion ependymoma that has been extensively treated. These data will be compiled as preliminary data regarding efficacy of marizomib as a salvage regimen for patients with heavily pretreated non-*RELA*-fusion ependymoma.

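### The primary endpoint, PFS6, has two different time origins, and no settled rule for deaths clearly unrelated to the tumour

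*Combined protocol and SAP*

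**What the plan says.** **Time origin.** Section 6.3.6: "Progression free survival will be defined from the time of registration to the time of confirmed progression". Section 6.3.7 uses the same start for OS: "Defined as the time from registration to the time of death". Section 10.1.1 defines PFS6 as the proportion of patients who are "progression-free at 6 months timepoint after initiation of treatment", and 10.1.2 also starts PFS12, median PFS and OS when treatment begins. Section 2.3 says only that registration "will take place per CCR SOP ADCR-2". That SOP is not part of the documents, and no maximum interval between registration and first dose is stated.

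**Event.** Section 6.3.6 names progression alone. The progression definition in 6.3.3 includes "failure to return for evaluation due to death or deteriorating condition (unless clearly unrelated to this cancer". Section 10.1.1 does not mention death. Section 10.1.2 describes median PFS for Cohorts 1-4 as the "median amount of time subject survives without disease progression after initiation of treatment". Time to treatment failure in 6.3.1 does list death from any cause, but that is a separate endpoint.

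**Confirmation.** Section 6.3.6 requires progression to be confirmed. Section 6.3.3 asks for confirmatory scans only after an objective response, and both sections let patients with unclear progression continue on trial.

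**Use.** Section 10.4.4: "If 4 or more patients are progression free at 6 months, we proceed to stage 2". At stage 2, 9 or more of 16 in Cohort 3 supports the claim for non *RELA*-fusion disease. Section 10.4.1 adds that a "Kaplan-Meier curve will be used to estimate the PFS6", without an event or censoring rule.

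**The concern.** Two analysts could each follow an operative section of the plan and score the same patient differently.

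- **Origin.** Registration comes before first dose. Counting 6 months from registration therefore stops the clock earlier in treatment and makes PFS6 look better.
- **Unrelated death before 6 months.** Under 6.3.6 with 6.3.3 this is not a progression. Under the 10.1.2 wording it ends PFS. The patient has no settled score in the two counts and might be censored in the Kaplan-Meier analysis.
- **Confirmed progression (secondary).** No procedure is given, and no rule says whether the PFS date is the assessment that first showed progression or the one that verified it.

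In Cohort 1 each patient is 1/9, or 11 percentage points, and a single patient can separate stopping from proceeding. With nine patients, this choice should not be left until outcomes are known.

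**Working it through.** **1. The plan's own stage 1 figures.** Inputs: n = 9 and threshold 4 (10.4.4); PFS6 0.30 unpromising and 0.60 promising (10.1). Formula: P(proceed) = P(X ≥ 4), X ~ Binomial(9, p).

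| True PFS6 | Quantity | Exact | Table 7 |
|---|---|---|---|
| 0.30 | early stopping | 0.7297 | 0.734 |
| 0.60 | early stopping | 0.0994 | 0.102 |
| 0.60 | effective for *RELA*-fusion | 0.9006 | 0.898 |

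The differences fit 10,000 simulations: the simulation standard error is √(0.7297 × 0.2703 / 10,000) = 0.004 at 0.30 and √(0.9006 × 0.0994 / 10,000) = 0.003 at 0.60. The reference value is therefore P(proceed) = 1 − 0.7297 = 0.270 at true PFS6 0.30.

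**2. Origin.** Assumptions: exponential PFS, progression dated continuously, 6 months = 182.6 days, and a gap g from registration to first dose. True PFS6 from first dose is p. Measured from registration it appears as p^((182.6 − g)/182.6). With p = 0.30:

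| g (days) | Exponent | Apparent PFS6 | P(≥ 4 of 9) |
|---|---|---|---|
| 0 | 1 | 0.300 | 0.270 |
| 7 | 0.962 | 0.314 | 0.303 |
| 14 | 0.923 | 0.329 | 0.339 |
| 28 | 0.847 | 0.361 | 0.418 |

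Progression is not in fact dated continuously. Section 6.3 relies mainly on imaging, and the Study Calendar (footnote 8) times MRI every 8 weeks from start of treatment. An on-time week-24 scan is day 168 from first dose, or day 168 + g from registration. With g = 14 that is day 182, still inside 6 months, so a progression first seen on that scan is classed the same way under both origins. For gaps up to about two weeks the real effect is therefore likely smaller than the table shows. This does not extend to long gaps: with g = 28 the same scan falls on day 196 from registration, past the cut-off. The calendar gives no window for MRI, so late scans would need a further assumption.

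**3. Clearly unrelated deaths.** Let q be the assumed share of patients who die of clearly unrelated causes before 6 months without progression. If these deaths are failures, the success probability is p; if they are scored as progression-free, it is p + q.

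| q | P(≥ 4 of 9), p = 0.30 | P(≥ 4 of 9), p = 0.60 |
|---|---|---|
| 0 | 0.270 | 0.901 |
| 2% | 0.317 | 0.921 |
| 5% | 0.391 | 0.946 |
| 10% | 0.517 | 0.975 |

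**4. How often one patient could decide.** A single reclassification matters only when the count is one short.

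- P(X = 3 of 9) = 0.267 at 0.30 and 0.074 at 0.60.
- P(X = 8 of 16) = 0.049 at 0.30 and 0.142 at 0.60.

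These are probabilities of standing at the boundary. A changed decision also needs a patient whose score depends on the definition.

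**5. Confirmation.** No size is computed. Section 6.3.5 dates progression at its first objective documentation, but only for duration of response.

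**The case against.** **Section 10.1.1 is the specific rule for the primary endpoint, and MRI is timed from treatment start, so first dose is the natural reading.** This is a fair reading and limits the practical effect. But no section gives 10.1.1 precedence over 6.3.6, and 10.1.1 settles neither unrelated deaths nor confirmation.

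**For PFS6 itself, no two sections openly contradict each other on unrelated deaths.** Largely right. The any-death reading comes from the median PFS bullet, a secondary endpoint. For PFS6 the defect is an event definition in 6.3.6 that omits death, together with silence in 10.1.1.

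**A reader might infer that the plan ignores all deaths, or counts dead patients as successes.** The documents do not support either. Section 6.3.3 makes failure to return because of death a progression unless clearly unrelated to the cancer. For the remaining deaths it only withholds that label; it also has an Unknown status, and no passage scores such a patient as progression-free. The death scenario in the working is one possible reading, not the stated rule.

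**A reader might also take the undefined confirmation as a contradiction.** It is not one. Sections 2.2.2.1 and 3.6 speak of confirming progression at screening by MRI, so 6.3.6 may mean no more than documented progression. What is missing is a statement to that effect and a dating rule for PFS.

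**Registration is a legitimate origin.** True. The fault lies in having two. Choosing first dose also leaves patients registered but never dosed without a rule, so the fix must supply one.

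**Conclusion.** The point holds and should be fixed. The firmest part is the origin: 6.3.6 and 6.3.7 use registration, 10.1.1 and 10.1.2 use start of treatment, and nothing reconciles them. The treatment of clearly unrelated deaths is unsettled for the endpoint behind both decision rules. Confirmation of progression is a secondary gap.

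The size is conditional on gaps, death shares and an exponential form that the documents do not supply. Within the assumed ranges, the chance of proceeding at true PFS6 0.30 moves from 0.270 to between 0.303 and 0.418 for the origin, and to between 0.317 and 0.517 for deaths scored as progression-free. The calculations do not show that a decision would be reversed or that the trial is biased: if the gap is short, treatment start is used, no unrelated death occurs and no progression near 6 months turns on when it was verified, the effect may be nil.

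**What to change.** Use one definition in 6.3.6, 10.1.1 and 10.1.2: time from first dose to first documented RANO progression or death from any cause, whichever comes first, with progression dated at the assessment that first showed it even if verified later. First dose is the origin 10.1.1 already uses and the one the MRI schedule follows.

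Also:
- count any death before 6 months as a failure in the 4-of-9 and 9-of-16 rules;
- give OS in 6.3.7 the same origin;
- state that patients registered but never dosed are reported separately and are not in the counts.

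As an editorial correction only, the median PFS bullet for Cohorts 2 and 4 in 10.1.2 repeats the OS wording and should refer to survival without progression. The intent is clear from 1.1.2 and 10.4.2, and PFS6 is unaffected.

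Cost: wording only. Thresholds and sample size stay as they are, and dosing records and survival follow-up already supply the dates. The downside is that PFS6 may come out slightly less favourable.

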6.3.7 Overall survival

Overall survival: Defined as the time from registration to the time of death

6.4 TOXICITY CRITERIA

The following adverse event management guidelines are intended to ensure the safety of each patient while on the study. The descriptions and grading scales found in the revised NCI Common Terminology Criteria for Adverse Events (CTCAE) version 5.0 will be utilized for AE reporting. All appropriate treatment areas should have access to a copy of the CTCAE version 5.0. A copy of the CTCAE version 5.0 can be downloaded from the CTEP web site (https://ctep.cancer.gov/protocolDevelopment/electronic_applications/ctc.htm#ctc_50).

The safety assessments will be performed according to the Study Calendar, Section 3.6.

7 NIH REPORTING REQUIREMENTS / DATA AND SAFETY MONITORING PLAN

7.1 DEFINITIONS

Please refer to definitions provided in Policy 801: Reporting Research Events found [here](#).

7.2 OHSRP OFFICE OF COMPLIANCE AND TRAINING/IRB REPORTING

7.2.1 Expedited Reporting

Please refer to the reporting requirements in Policy 801: Reporting Research Events and Policy 802 Non-Compliance Human Subjects Research found [here](#). Note: Only IND Safety Reports that meet the definition of an unanticipated problem will need to be reported per these policies.

7.2.2 IRB Requirements for PI Reporting at Continuing Review

Please refer to the reporting requirements in Policy 801: Reporting Research Events found [here](#).

7.3 NIH REQUIRED DATA AND SAFETY MONITORING PLAN

7.3.1 Principal Investigator/Research Team

The clinical research team will meet on a regular basis (once a week) when patients are being actively treated on the trial to discuss each patient.

All data will be collected in a timely manner and reviewed by the principal investigator. Events meeting requirements for expedited reporting as described in section 7.2.1 will be submitted within the appropriate timelines.

The principal investigator will review adverse event and response data on each patient to ensure safety and data accuracy. The principal investigator will personally conduct or supervise the investigation and provide appropriate delegation of responsibilities to other members of the research staff.

8 SPONSOR SAFETY REPORTING

8.1 DEFINITIONS

8.1.1 Adverse Event

Any untoward medical occurrence in a patient or clinical investigation subject administered a pharmaceutical product and which does not necessarily have a causal relationship with this treatment. An adverse event (AE) can therefore be any unfavorable and unintended sign (including an abnormal laboratory finding), symptom, or disease temporally associated with the use of a medicinal (investigational) product, whether or not related to the medicinal (investigational) product (ICH E6 (R2))

8.1.2 Serious Adverse Event (SAE)

An adverse event or suspected adverse reaction is considered serious if in the view of the investigator or the sponsor, it results in any of the following:

- Death,
- A life-threatening adverse event (see section **8.1.3**)
- Inpatient hospitalization or prolongation of existing hospitalization
 - A hospitalization/admission that is pre-planned (i.e., elective or scheduled surgery arranged prior to the start of the study), a planned hospitalization for pre-existing condition, or a procedure required by the protocol, without a serious deterioration in health, is not considered a serious adverse event.
 - A hospitalization/admission that is solely driven by non-medical reasons (e.g., hospitalization for patient convenience) is not considered a serious adverse event.
 - Emergency room visits or stays in observation units that do not result in admission to the hospital would not be considered a serious adverse event. The reason for seeking medical care should be evaluated for meeting one of the other serious criteria.
- Persistent or significant incapacity or substantial disruption of the ability to conduct normal life functions
- A congenital anomaly/birth defect
- Important medical events that may not result in death, be life-threatening, or require hospitalization may be considered a serious adverse drug experience when, based upon appropriate medical judgment, they may jeopardize the patient or subject and may require medical or surgical intervention to prevent one of the outcomes listed in this definition.

8.1.3 Life-threatening

An adverse event or suspected adverse reaction is considered "life-threatening" if, in the view of either the investigator or sponsor, its occurrence places the patient or subject at immediate risk of death. It does not include an adverse event or suspected adverse reaction that, had it occurred in a more severe form, might have caused death. (21CFR312.32)

8.1.4 Severity

The severity of each Adverse Event will be assessed utilizing the CTCAE version 5.0

8.1.5 Relationship to Study Product

All AEs will have their relationship to study product assessed using the terms: related or not related.

- Related – There is a reasonable possibility that the study product caused the adverse event. Reasonable possibility means that there is evidence to suggest a causal relationship between the study product and the adverse event.
- Not Related – There is not a reasonable possibility that the administration of the study product caused the event.

8.1.6 Events of Clinical Interest (ECI) – CNS adverse events

Marizomib is known to cause CNS AEs (e.g., hallucinations - visual more common than auditory, confusion, mental status changes, delirium, etc.) ranging in severity from Grade 1 to Grade 4.

8.2 ASSESSMENT OF SAFETY EVENTS

AE information collected will include event description, date of onset, assessment of severity and relationship to study product and alternate etiology (if not related to study product), date of resolution of the event, seriousness and outcome. The assessment of severity and relationship to the study product will be done only by those with the training and authority to make a diagnosis and listed on the Form FDA 1572 as the site principal investigator or sub-investigator. AEs occurring during the collection and reporting period will be documented appropriately regardless of relationship. AEs will be followed through resolution.

SAEs will be:

- Assessed for severity and relationship to study product and alternate etiology (if not related to study product) by a licensed study physician listed on the Form FDA 1572 as the site principal investigator or sub-investigator.
- Recorded on the appropriate SAE report form, the medical record and captured in the clinical database.
- Followed through resolution by a licensed study physician listed on the Form FDA 1572 as the site principal investigator or sub-investigator.

For timeframe of recording adverse events, please refer to section **6.1**. All serious adverse events recorded from the time of first investigational product administration must be reported to the sponsor.

